## Protocol Amendment 2 (16-DEC-2019)

### Protocol Amendment 2 Summary of Changes Specific to Sub-study 1

Section # and Name	Description of Change	Brief Rationale
Revised Study Design		
Section 11.2, 11.13.1	Updated pregnancy wording: follow up timing and management of pregnancy.	Program level changes
Safety Changes		
Section 11.2	Ophthalmology wording updated throughout the protocol. Changes in the frequency of assessments. The GSK scale removed, steroid eye drops not mandatory and corneal images no longer required. Updated stopping criteria based on ocular examination findings	Updated in line with program level changes.
Section 11.2 SoA tables	Updated timing of SAE assessments.	Updated timing of SAE assessments in line with program.
Changes in Assessments and SoAs		
Section 11.2, Table 21, Table 22	CRP assessment removed from SoA tables	
Section 11.2	Removed physical exam and vital sign assessment from SoA table of assessments to be done regardless of dosing (and updated footnote numbering)	These evaluations are done with dosing
Section 11.2, Table 23 and 24	Removed AESI assessment.	This is covered under AE's and SAEs. This is still being collected.

Section # and Name	Description of Change	Brief Rationale
Section 11.2, Table 23	Clarification around timings for biomarker samples.	Clarifications
Protocol Clarification and Alignment		
Section 11.6	Added wording that "Sponsor may decide not to evaluate all dose levels based on data external to this study..."	Clarity of wording around when a sub-study can be closed
Section 11.7, Table 26	Infusion timing of belantamab mafodotin and GSK'998 (OX40) added	Regulatory Agency request. Infusion timings added
Section 11.4	Rationale for combination of belantamab mafodotin with GSK'998 (aOX40) preclinical wording clarified	Regulatory Agency request for clarified wording
Section 11.13	Clarification around wording for the administration of GSK'998 only to be administered with GSK'916 with the possibility of GSK'998 administration 1 day later than GSK'916 in the case of an IRR on the date of GSK'916 infusion and the maximum treatment delay for GSK'998.	Regulatory Agency request for clarified wording

### Protocol Amendment 1 (24-JUN-2019)

The protocol was amended in line with comments from the regulatory agency which included the following:

- More preclinical data included to provide the biological rationale for the use of belantamab mafodotin in combination GSK'988 (aOX40).
- Lower starting doses for GSK'988 (aOX40).
- Note: belantamab mafodotin is referred to as GSK'916 only for the purposes of Laboratory samples.
- Note: GSK'998 (aOX40) is referred to as GSK'998 only for the purposes of Laboratory samples.

Section # and Name	Description of Change	Brief Rationale
Revised Study Design		
Section 11.3 Rationale for combination of belantamab mafodotin with GSK'998 (aOX40)	Additional pre-clinical data added, and wording clarified	Amended to include further details regarding the preclinical studies that were conducted to support the investigation of specific combinations in patients with multiple myeloma. As requested by the FDA
Section 11.4 Dose justification for GSK'998 (aOX40)	Starting dose of GSK'998 (aOX40) lowered from 24 mg IV to 8 mg IV Q3W considered equivalent to the 0.1 mg/kg dose in the ongoing FTIH trial [NCT02528357], assuming a median participant weight of 80 kg.	As requested by the FDA to include a lower starting dose
Section 11.4.1 Clinical Activity of GSK'998 (aOX40) monotherapy	Added dose of GSK'998 administered.	As requested by the FDA
Section 11.5 Dose Exploration of Combination Treatment belantamab mafodotin Co-Administered with GSK'998 (aOX40)	Updated the dose exploration schema for belantamab mafodotin in combination with GSK'998 (aOX40).	As requested by the FDA
Section 11.7.2 Permitted Dose Reductions for belantamab mafodotin when in combination with GSK'998 (aOX40)	Modified permitted dose reductions for belantamab mafodotin when in combination with GSK'998 (aOX40) in Table 26 and text.	Clarification in line with FDA request
11.7.3 Permitted Dose Modifications of GSK'998 (aOX40) when in combination with belantamab mafodotin	Revised text on permitted dose modifications.	Clarification
Changes in Assessments and SoAs		
Section 11.1 Table 19	Clarified timings Added screening thyroid function tests	Clarification of wording and timings, and addition of missing tests

Section # and Name	Description of Change	Brief Rationale
Section 11.1 Table 20	
Clarified timings/wording
 
Clarified AE/SAE timings to agree with text in the protocol:
 
“AEs will be assessed up to 45 days post the last dose. SAEs will be assessed up to 90 days post last dose, or 45 days post last dose if the participant initiates a new anticancer therapy (whichever is shorter). All related SAEs are to be collected from first dose through OS follow-up”
 
Spot urine (albumin/creatinine ratio) removed
	Clarification of wording and timings and removal of tests
Section 11.1 Table 21	
Clarified timings/wording of PK, ADA, GSK'916, sBCMA samples
 
Day 4 Cycle 1 column added for clarity
 
“Ocular Examination” removed (to avoid confusion, this is carried out every 3 weeks regardless of dosing).
 
ECOG performance status added
 
Deleted reference to EDTA tube & PAXgene tube
	Clarification of wording and timings, removal/addition of tests and other edits for consistency between the SoA tables

## Version history

SAP Version	Approval Date	Protocol Version (Date) on which SAP is Based	Change	Rationale
SAP		PA5 (21-JAN-2022)	Not Applicable	Original version

## 1. INTRODUCTION

The purpose of this SAP is to describe the planned analyses to be included in the CSR for Study 208887 sub-study 1. For more details about the statistical analysis and plan for the overall study refer to the Master SAP. This sub-study was terminated early in the Dose Exploration (DE) phase; therefore, this sub-study SAP will focus only on this DE phase.

### 1.1. Changes to Protocol Defined Analyses

Effective October 2020, GSK made the decision to close this sub-study at the DE phase. The data demonstrate that the participants in the aOX40 sub-study had negligible benefit from the combination, which could not be explained by known factors. As a result, all analyses corresponding to the Cohort Expansion (CE) phase, as well as the analysis of exploratory endpoints will not be performed.

Changes from the originally planned statistical analysis specified in the protocol are detailed in Table 1.

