### **2.2.1. Clinical pharmacology data with GSK'998**

As of a clinical data cut-off date of 13 Aug 2017, a total of 82 participants with advanced solid tumors have been treated in the ongoing FTIH study 201212. Forty-five received monotherapy GSK'998 (aOX40) at doses between 0.003-10 mg/kg intravenously (IV) once every 3 weeks

In Study 201212, the PK of GSK'998 (aOX40) administered as single-agent monotherapy was evaluated after IV administration at doses of 0.003 mg/kg to 10 mg/kg every 3 weeks in patients with solid tumors.

The GSK'998 (aOX40) concentration-time profiles [GlaxoSmithKline Document Number 2014N212091\_05, 2018] initially exhibited a bi-exponential decline typical for IV-administered mAbs. At lower GSK'998 (aOX40) concentrations, faster elimination and shorter half-lives were observed, indicating target-mediated disposition. Consequently, AUC and trough concentrations were increasing more than proportionally with dose. GSK'998 (aOX40) Cmax values normalized by dose for Cycle 1 indicated dose-proportionality for Cmax and Cmax values were typical for mAbs.

At a data cut-off date of 22 Jun 2017, 49% of participants with available post-treatment data tested positive for anti- GSK'998 (aOX40) anti-drug antibodies (ADA) across dose levels 0.003–10 mg/kg GSK'998 (aOX40) in Part 1A (monotherapy) and 0.003–0.1 mg/kg in Part 2A (combination therapy). Positive ADA titers were detectable as early as 3 weeks after the first dose of GSK'998 (aOX40). Of the 30 participants with positive ADA titres, two participants experienced infusion related reactions beginning with administration of the third dose of GSK'998 (aOX40); no other infusion reactions have been reported in the study to date.

Receptor occupancy (RO) was assessed for peripheral blood CD3+ T cells in study 201212. Preliminary data indicated that a high degree ( $\geq 80\%$ ) of receptor occupancy is achieved initially ( $\leq 1$  day after dosing) even for the lowest dose of 0.003 mg/kg GSK'998 (aOX40). For doses of 0.1 mg/kg or smaller, receptor occupancy subsequently declines towards the end of the dosing cycle. At doses of GSK'998 (aOX40) 0.3 mg/kg or greater, continuously high receptor occupancy levels are observed over the whole 21-day dosing cycle.

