**4.2. Scientific Rationale for Study Design****4.3. Justification for Dose**

GSK'998 (aOX40) will initially be administered at a flat dose of 8 mg IV Q3W on Day 1 of each 21-day cycle after the infusion with belantamab mafodotin. Please refer to 208887 MP Section 4.3 for starting dose of belantamab mafodotin.

Previous clinical experience for GSK'998 (aOX40) in Study 201212 [NCT02528357] was based on weight-proportional dosing. The 8 mg dose to be tested in this study is considered equivalent to the 0.1 mg/kg dose in the ongoing FTIH trial [NCT02528357], assuming a median participant weight of 80 kg.

The 8-mg dose of GSK'998 (aOX40) is considered an appropriate dose for combination therapy with belantamab mafodotin based on the following: According to currently available data, the starting dose of 8 mg was well tolerated and did not result in excessive toxicity in advanced solid tumor patients. Doses up to 10 mg/kg (800 mg equivalent) GSK'998 (aOX40) monotherapy tested in the ongoing FTIH trial [NCT02528357] did not result in DLTs and an MTD was not established. To date, there is no apparent dose-toxicity response with GSK'998 monotherapy. The starting dose of 8 mg results in exposure approximately 100-fold lower than the 10 mg/kg dose.

In the ongoing FTIH trial in participants with advanced solid tumors [NCT02528357] the GSK'998 dose level of 0.1 mg/kg (equivalent to 8 mg) represents one dose level below the dose (0.3 mg/kg, equivalent to 24 mg) that demonstrated linear PK, saturation of peripheral OXO40 RO across the dosing interval, and clinical activity. No clinical activity was observed for GSK'998 monotherapy 0.1 mg/kg in participants with solid tumors; however, evidence of some pharmacological target engagement was observed, with ~30% RO by Week 3 post-dose compared ~85% RO for the 0.3 mg/kg dose level. GSK'998 0.1 mg/kg trough plasma concentrations dropped below the level of quantification by Week 3, whereas 0.3 mg/kg trough concentrations remained measurable. Thus, an 8 mg (0.1 mg/kg equivalent) dose of GSK'998 is considered to balance appropriate tolerability with the potential for exposing participants to subtherapeutic doses.

Based on the large capacity, non-specific clearance, and recycling mechanisms for mAbs, no DDI related to non-specific IgG turnover is expected between belantamab mafodotin and GSK'998 (aOX40) for the dose ranges considered.

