##### 4.1.4. Examination of Covariates, Other Strata and Subgroups

As this sub-study was terminated during the DE phase, covariates, other strata, and subgroups are not applicable as these would have been used in the CE phase only.

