### **4.3. Secondary Endpoint(s) Analyses**

Due to this sub-study being terminated early during the DE phase, there will be no primary efficacy analysis for the CE phase as these data were not collected.

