### **4.4. Exploratory Endpoints Analyses**

Analysis of exploratory endpoints will be performed for neither the DE nor the CE phase, due to the early termination of aOX40.

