#### **4.6. Other Analyses**

No POPPK, exploratory biomarker, or PD analyses will be conducted. For this sub-study there will also be no health-related quality of life analysis due to early termination.

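### Does the remark that negligible benefit had no known explanation oblige the SAP to relate response to aOX40 exposure?

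*SAP*

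**What the plan says.** SAP section 1.1 dates the closure decision to October 2020 and gives the reason: "The data demonstrate that the participants in the aOX40 sub-study had negligible benefit from the combination, which could not be explained by known factors". It then says that the cohort expansion (CE) analyses "as well as the analysis of exploratory endpoints will not be performed".

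Later sections confirm that the cancellation covers dose exploration (DE):

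- SAP 4.1.4: "covariates, other strata, and subgroups are not applicable as these would have been used in the CE phase only".
- SAP 4.4: "Analysis of exploratory endpoints will be performed for neither the DE nor the CE phase, due to the early termination of aOX40".
- SAP 4.6: "No POPPK, exploratory biomarker, or PD analyses will be conducted".

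For CE the SAP gives a data reason in section 4.3: "there will be no primary efficacy analysis for the CE phase as these data were not collected". For the DE exploratory endpoints it gives only early termination for lack of efficacy (Table 1 and section 4.4).

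Some outputs stay. Confirmed best response is summarised and listed with exact 95% intervals (4.3.1, 4.3.2). Treatment exposure has a listing by participant (4.5.1). PK and ADA are analysed under the Master SAP (4.6.1, 4.6.2). The displays are labelled by dose level (4.1.2.1).

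On the partner dose, Protocol section 4.3 equates 8 mg with 0.1 mg/kg at 80 kg and describes the choice as a balance between tolerability and "the potential for exposing participants to subtherapeutic doses". Protocol section 2.2.1 reports that at 0.3 mg/kg or more "continuously high receptor occupancy levels are observed over the whole 21-day dosing cycle".

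**The concern.** Saying that known factors do not explain a result implies that some were examined. This SAP describes no examination: there are no covariates, subgroups, biomarker analyses or PD analyses, and PK and ADA are reported apart from response. Dose level cannot stand in for partner dose, because both opened levels used 8 mg and the 24 mg level was never started.

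The protocol supplies an obvious candidate factor. At the equivalent of 8 mg it reports no monotherapy activity in solid tumours and about 30% receptor occupancy by Week 3, against about 85% at 0.3 mg/kg. If the clause were carried into the clinical study report, a reader might conclude that low partner exposure had been ruled out when no planned display addresses it. The plan also appears to drop DE analyses for which samples were scheduled, without saying whether the samples were assayed.

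**Working it through.** The SAP gives no figure for this point, so there is none to reproduce. The check asks what role the sentence plays, and what a display joining response to exposure could show.

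**1. Role of the sentence.** It stands in the section on changes to planned analyses and explains a decision already taken. It sets no endpoint, test or display. SAP section 2 states that no formal hypothesis is tested in DE. Protocol section 4.4.2 allows a sub-study to close during DE for too few responders. Neither the closure nor any retained analysis depends on the clause.

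**2. Partner dose received.** SAP section 5 gives 6 + 3 = 9 participants, all assigned 8 mg. In mg/kg:

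- 8/80 = 0.10 at the protocol's assumed weight.
- 8/50 = 0.16 and 8/120 = 0.067 at assumed extremes of 50 kg and 120 kg.
- 8 mg reaches 0.3 mg/kg only at 8/0.3 = 26.7 kg or less.

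Across this weight range, everyone was below the dose with sustained high occupancy. This follows from the assigned dose and needs no listing.

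**3. Expected trough values.** Protocol section 4.3 reports that troughs at 0.1 mg/kg were below quantification by Week 3, while those at 0.3 mg/kg stayed measurable. A Dose 2 predose column would therefore be expected to be below quantification at about 80 kg and above. Lighter participants fall between the two doses, where the documents give no result. A nearly constant column cannot separate participants by exposure. ADA status does not measure exposure.

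**4. What 9 participants can show.** The responder count is not in the documents, so a range is needed. With r responders and no ties, the smallest two-sided exact rank-sum p-value is 2/C(9, r):

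| Responders | Smallest p |
|---|---|
| 0 | not estimable |
| 1 | 2/9 = 0.222 |
| 2 | 2/36 = 0.056 |
| 3 | 2/84 = 0.024 |

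Reaching 0.05 needs at least 3 responders and at least 3 non-responders. Tied values below quantification make it harder. A description of negligible benefit points to the top of the table.

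**5. Precision already conveyed.** The planned exact intervals show how little 9 participants establish. If there were no responders, the upper 95% limit would be 1 − 0.025^(1/9) = 33.6%. By dose level it would be 45.9% for 0/6 and 70.8% for 0/3. The chance of 0/9 is 0.8^9 = 13.4% at a true response rate of 20%, and 0.7^9 = 4.0% at 30%.

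**6. What the cancellation removes.** aOX40 concentration and ADA are secondary endpoints and are kept. Biomarker analysis is the only exploratory analysis SAP Table 1 names. The documents do not show that any cancelled analysis would have related response to partner exposure.

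**The case for a change.** The best case for acting is that the remedy is cheap. It would be one descriptive table of 9 rows, a Table 1 entry separating CE from DE exploratory analyses, and a sourced or softened sentence. The word for what the data show is strong for 9 participants. Protocol section 2.3.2 says the study's data may help identify who benefits. The schedule in Protocol Table 4 lists 6 cytokine, 5 RNA and 6 cryopreserved-cell draws through Dose 4, so up to 17 × 9 = 153 draws could go unanalysed.

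Part of this stands. The clause has no stated basis, and no display planned in this SAP puts response beside partner concentration or ADA.

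The rest is weaker:

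- The sample count comes from Amendment 4, dated December 2020, after the October 2020 closure. Earlier amendments changed sampling times, so the schedule these participants followed is not established.
- The SAP does give a reason for dropping the DE exploratory work. Stopping it after 9 participants and a decision to close is a fair trade-off.
- Non-use of the 24 mg level is already stated twice in the SAP (1.3 and 4.1.2.1).
- Response and treatment exposure are listed, and PK and ADA are reported under the Master SAP. If those outputs include listings, 9 records can be aligned by hand.
- Low aOX40 exposure might explain missing added benefit, but not a poor response to a regimen in which everyone was also assigned belantamab mafodotin. With no monotherapy column in DE, the two cannot be separated by any arrangement of these data.

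**Conclusion.** No change to the plan is needed. The clause in SAP 1.1 is unsourced and somewhat too firm, but it reports why the sponsor closed the sub-study and directs no analysis. Rewording it, or splitting a Table 1 row, would record a rationale and leave every planned result as it is. A joined listing would rearrange largely retained data and could neither confirm nor exclude an exposure effect. Its trough column would probably show little variation. Anyone wanting to look at exposure could set earlier samples, such as Day 8 if collected, beside best response without a SAP change. Authors of the study report can cite the review behind the clause or leave it out.

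This rests on three assumptions: weights of roughly 50 to 120 kg, solid-tumour trough findings that carry over to myeloma, and a low responder count, which the documents do not give. The Master SAP was not available. If it already contains a linked display, the point falls away entirely.

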## 1.1. Synopsis

Enhanced antigen presentation through ICD and resulting T cell-mediated durable immunity, suggests that additional therapeutic benefit can be obtained from combination treatment of belantamab mafodotin with immune-enhancing agents such as GSK'998 (aOX40). Murine aOX40 (OX86) in combination with belantamab mafodotin provided with survival benefit in mice over GSK'916 single agent activity, although, it did not reach statistical significance. In addition, the combination of OX86 at 0.2, 1 and 5 mg/kg with belantamab mafodotin resulted in 7, 4 and 5 (out of 10 mice) tumor free survivors.

This is a randomized Phase I/II, open-label, platform-design study of belantamab mafodotin in combination with GSK'998 (aOX40) treatment compared to belantamab mafodotin monotherapy in participants with RRMM. Overall design is in relation to the dose exploration of combination treatment.

There will be a dose exploration (DE) phase which will evaluate the safety and tolerability profile of belantamab mafodotin when administered in combination with other anti-cancer treatments. The number of dose levels explored will vary per sub-study, and up to 10 participants per dose level will be evaluated for safety and preliminary efficacy. A recommended Phase 2 dose (RP2D) for each combination treatment will be identified based on the safety and preliminary efficacy in DE. This will be followed by a cohort expansion (CE) phase which will evaluate the clinical activity of the combination treatment in comparison to monotherapy belantamab mafodotin in additional participants with RRMM at the RP2D in sub-studies.

A total of 3 dose levels can be potentially evaluated, so there could potentially be a maximum of 3 dosing cohorts running simultaneously in the dose exploration (DE) phase. The starting dose of belantamab mafodotin will be 1.9 mg/kg and the starting dose of GSK'998 (aOX40) will be 8 mg every 3 weeks. Please see 208887 MP Section 4.1.1 for details of decision making during the DE phase.

Sub-study 1 has been closed to enrollment.

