**Table 1 Changes to Protocol Defined Analysis Plan**

Protocol Defined Analysis	SAP Defined Analysis	Rationale for Changes

 
• Exploratory analyses                             
 
○ Biomarker analysis
 
 
 
• Interim analysis for DE phase
 
• All analysis related to CE phase
 
	The listed protocol defined analyses will not be included in this sub-study.	This sub-study was terminated during DE phase due to observed lack of efficacy.

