### 1.3. Study Design

Overview of Study Design and Key Features													
Please refer to the 208887 Master SAP for overall Study Design for the study													
Design Features	
 
Refer to the 208887 Master SAP for the key design feature for the study
 
												
Dosing	
 
The Starting Dose (SD) for belantamab mafodotin in study 208887 will be 1.9 mg/kg Q3W in combination with aOX40
 
GSK'998 (aOX40) will initially be administered at a flat dose of 8 mg IV Q3W on Day 1 of each 21-day cycle after the infusion with belantamab mafodotin.
 
 
  
 Dose level	Belantamab mafodotin dose	GSK'998 (aOX40) dose	
   
 1 (starting dose level)	1.9 mg/kg	8 mg	
 
 2	2.5 mg/kg	8 mg	
 
 3	2.5 mg/kg	24 mg	
  
 
Note: Dose level 3 was not initiated in this sub-study due to the study being terminated early in the DE phase.
	Dose level	Belantamab mafodotin dose	GSK'998 (aOX40) dose	1 (starting dose level)	1.9 mg/kg	8 mg	2	2.5 mg/kg	8 mg	3	2.5 mg/kg	24 mg
Dose level	Belantamab mafodotin dose	GSK'998 (aOX40) dose											
1 (starting dose level)	1.9 mg/kg	8 mg											
2	2.5 mg/kg	8 mg											
3	2.5 mg/kg	24 mg											
Time & Events	
 
Refer to Section 1.3: Schedule of Activities (SoA) in Sub-study 1 modular protocol
 
												
Treatment Assignment	
 
In DE phase, treatments will be assigned to participants with predefined algorithm.
 
												
Interim Analysis	
 
The Interim Analysis (IA) planned in the DE will not be carried out.
 
												
Blinding	
 
This is an open label study.
 
In DE phase, participants will be assigned to available treatment slots by a predetermined algorithmic approach.
 
												

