## 2. STATISTICAL HYPOTHESES

In the DE Phase, the primary objective is to determine the safety and tolerability of belantamab mafodotin and aOX40. No formal statistical hypothesis will be tested.

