##### 4.1.2.1. Study Treatment & Sub-group Display Descriptors

Phase	Description
DE	1.9mg/kg GSK916+8mg aOX40
	2.5mg/kg GSK916+8mg aOX40
	2.5mg/kg GSK916+24mg aOX40 

 Note that this dose level was not used due to early termination

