#### **4.3.1. Key Secondary Endpoint**

For the definition of the key secondary endpoint, ORR, along with the derivation of confirmed response table please refer to Section 4.2.2.1 of the MSAP.

A summary of investigator assessed best response with confirmation will be produced, using the Safety population.

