#### **4.3.2. Secondary Endpoints**

Best Overall Response (BOR) rates (i.e Partial Response (PR) rate, Very Good Partial Response (VGPR) rate, Complete Response (CR) rate and Stringent Complete Response (sCR) rate) will be reported within the summary table described in Section 4.3.1.

The derivation of confirmed response table in Section 4.2.2.1 of the MSAP, will be used confirm the secondary endpoints.

BOR and corresponding response rates will be summarized using descriptive statistics and listed. The corresponding 95% exact CI will also be provided. Participants with unknown or missing responses will be treated as non-responders, i.e., these participants will be included in the denominator when calculating percentages of response.

Other secondary endpoints, PK, ADAs, and AESIs can be found in the sections below.

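### Does SAP 1.1 need rewording, or a pooled response rate added, because it reads negligible benefit from at most nine uncontrolled participants?

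*SAP*

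**What the plan says.** SAP Section 1.1 gives the reason for closing the sub-study in October 2020: "The data demonstrate that the participants in the aOX40 sub-study had negligible benefit from the combination, which could not be explained by known factors". It then drops the cohort expansion (CE) analyses and the exploratory endpoints. Table 1 in the same section gives the reason in milder terms: "This sub-study was terminated during DE phase due to observed lack of efficacy".

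The remaining passages set the frame:

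- Protocol 1.1 (Synopsis) leaves it to CE to "evaluate the clinical activity of the combination treatment in comparison to monotherapy belantamab mafodotin". DE has combination dose levels only.
- SAP 2, on DE: "No formal statistical hypothesis will be tested".
- SAP 5 reports six participants at dose level 1 and three at dose level 2. SAP 1.3 adds: "Dose level 3 was not initiated in this sub-study".
- SAP 4.7 cancels the interim look at overall response rate (ORR), because neither level reached ten participants.
- SAP 4.3.1: "A summary of investigator assessed best response with confirmation will be produced, using the Safety population". SAP 4.3.2 adds a listing, counts missing responses as non-responses, and states: "The corresponding 95% exact CI will also be provided".
- SAP 4.1.2.1 lists display descriptors by dose level, such as "2.5mg/kg GSK916+8mg aOX40", and names no total.
- Protocol 4.4.2 allows a sub-study to close during DE when too few responders are seen.

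**The concern.** To say that data demonstrate a lack of benefit from a combination normally implies a comparison, or at least an estimate precise enough to exclude a worthwhile effect. DE offers neither. The sentence also claims that known factors do not explain the result, but it names none, and SAP 4.1.4 sets covariates and subgroups aside as not applicable. The sub-study SAP gives no responder count, number evaluable, cut-off date, reference rate or closure criterion.

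There is also a mismatch of unit. The sentence speaks of the sub-study participants as one group, whereas the descriptors are dose levels. If the response table showed only columns of six and three, it would contain no estimate for the group that the sentence describes. The risk is that the clinical study report repeats an efficacy conclusion that its own key secondary table is too small to carry.

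**Working it through.** **Inputs.** Enrolment is 6 and 3 (SAP 5), so N = 6 + 3 = 9. This agrees with SAP 4.7, where both levels fall short of ten. The confidence level is 95% (SAP 4.1.2). The interval is exact (SAP 4.3.2), taken here as Clopper-Pearson. The documents state no response rate, so there is no figure of the plan's own to reproduce. Responder counts of 0, 1 and 2, and the true response rates used below, are assumptions.

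**Step 1: exact intervals.** With no responder the lower limit is 0 and the upper limit is 1 − 0.025^(1/n):

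- n = 9: 1 − 0.025^(1/9) = 33.6%
- n = 6: 1 − 0.025^(1/6) = 45.9%
- n = 3: 1 − 0.025^(1/3) = 70.8%

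With x ≥ 1 responders, the limits are the 2.5% quantile of Beta(x, n − x + 1) and the 97.5% quantile of Beta(x + 1, n − x):

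- 1/9: 0.3% to 48.2%
- 2/9: 2.8% to 60.0%

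Full recruitment of one level would have changed little: 0/10 has an upper limit of 30.8%. The imprecision comes from the DE design, not mainly from stopping at nine.

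**Step 2: how surprising a low count would be.** P(X ≤ x) for X ~ Binomial(9, p). For example, P(X = 0) at p = 0.3 is 0.7^9 = 4.0%.

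| Responders of 9 | p = 20% | p = 30% | p = 40% |
|---|---|---|---|
| 0 | 13.4% | 4.0% | 1.0% |
| at most 1 | 43.6% | 19.6% | 7.1% |
| at most 2 | 73.8% | 46.3% | 23.2% |

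No responder in nine would be suggestive against a true rate of 30% or 40%. Two responders would be unremarkable at any rate shown. Whether the sentence is fair therefore turns on two numbers that the documents do not give: the count and a reference rate.

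**Step 3: what depends on the sentence.** The primary analysis (SAP 4.2), the response summary (SAP 4.3.1 and 4.3.2) and the safety analyses (SAP 4.5) do not use it as an input. CE is dropped because the sub-study closed, whatever words describe the closure. Rewording it changes no table and no estimate.

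**Step 4: is the total excluded?** SAP 4.3.1 and 4.3.2 define the response summary by the Safety population and do not mention dose level. SAP 4.1.2.1 includes a level that was never used, so it is a list of labels and not a literal column layout. A pooled reading is as open as a by-level one.

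**The case for a change.** The best case for a change is that a plan should not state an efficacy result before its own final analysis. SAP 4.1.1 places that analysis after database freeze. The SAP also describes one event at two strengths, and the weaker wording of Table 1 could replace the stronger one at almost no cost. The claim about known factors can be questioned from the protocol itself. Both levels tested used 8 mg of aOX40, and Protocol 4.3 reports no monotherapy activity in solid tumours at the dose it treats as equivalent. A sentence about the combination therefore reaches beyond the levels tested. A pooled column would bring the zero-responder upper limit down from 45.9% and 70.8% to 33.6%.

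Much of this stands as criticism of style. The verb is too strong for what is shown, and the known factors should ideally be named or left out. It does not carry further, for four reasons.

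- The sentence is in the past tense and concerns the participants observed. It can be read as a description of them, which confidence limits do not contradict.
- The proposed substitute is already in Table 1. With two responders it would be no better supported than the present sentence.
- Pooling is a choice. The two levels differ in belantamab mafodotin dose (1.9 and 2.5 mg/kg), and DE was planned by dose level. A fixed label of nine could also be wrong, because SAP 5 counts enrolled participants while the table uses the Safety population.
- Closure counts and criteria belong to a decision record or the study report. Their absence is not a fault in an analysis plan. Decision rules for DE are referred to Master Protocol Section 4.1.1, which was not available for this review.

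**Conclusion.** No change to the plan is needed. The arithmetic behind the concern is right: at most nine participants without a comparator cannot exclude a response rate of about one third even if nobody responded. But the wording governs no analysis, the documents do not show it to be false, and the same section already gives a more measured statement. The missing mention of a total column is at most a gap that analysts fill sensibly. The response categories are summarised with exact intervals and listed by participant, so no information is lost.

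This conclusion rests on assumed responder counts of 0 to 2, on reading the exact interval as Clopper-Pearson, and on the Safety population being no larger than the nine enrolled. The Master SAP and the displays document named in SAP 4.5.3 were not available and may already specify a total. The SAP is based on protocol amendment 5, whereas the sub-study protocol supplied is amendment 4, so a later account of the closure may also exist. Softening the verb would be a reasonable courtesy if the SAP were reopened for another reason, but it would alter no result.
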